12.4 Vital Signs and Weight

Vital signs comprise pulse rate, diastolic blood pressure (DBP), SBP, respiration rate, and temperature. Except for the Follow-up Visit, vital signs and weight will be measured at all study visits. CFBL and percent CFBL will be calculated for each vital sign and weight parameter at each time point (including end of treatment) and summarized by treatment group. Additionally, for DBP and SBP, the previous table will be presented by baseline hypertensive treatment status (yes or no) and treatment group.

Vital signs and weight will also be presented in a listing.

12.5 Physical Examinations

A full physical examination will be performed at each subject's first study visit (either at the Pre-Screening Visit or the Screening Visit) and last study visit (either at the Week 12 Visit or the ET Visit). At all other Study Visits (eg, Week 2) where a full physical examination was not conducted except the Follow-up Visit, a symptom-directed physical examination will be performed. Additionally, a symptom-directed physical examination will only be conducted at the Follow-up Visit for subjects who had an abnormal result at Week 12 (or the ET visit) or had an ongoing treatment-related AE.

For each assessment (general appearance, respiratory, etc.), the number and percentage of normal and abnormal findings will be provided by actual treatment group and visit for the SAS. The denominator used to calculate the percentage will be the number of subjects that underwent a physical examination at the corresponding visit.

13 OTHER RELEVANT DATA ANALYSES/SUMMARIES

13.1 Medical History

Medical history will be coded using MedDRA version 19.1. Medical history will be summarized by SOC and PT by actual treatment group for the SAS and will be presented in the listings. At each level of summarization, subjects who report one or more medical history events within a given level (SOC/PT) will only be counted once at that level. The table will be sorted by SOC (alphabetically) and then by PT (decreasing frequency in the gemcabene column within each SOC).

13.2 Prior and Concomitant Medications

Prior and concomitant medications will be coded using the World Health Organization (WHO) Drug Dictionary version 01 Mar 2016. A prior medication is defined as a medication with a stop date prior to the date of the subject's first dose (ie, medication stop date < date of first dose). A concomitant medication is defined as a medication with a start date on or before the date of the subject's last dose (ie, medication start date \leq date of last dose) and a stop date on or after the date of the subject's first dose (ie, medication stop date \geq date of first dose); thus, a medication that is ongoing at the time of the subject's first dose is considered concomitant. Partial and missing dates will be imputed using rules in [Appendix 2](#).

Prior and concomitant medications will be summarized in separate tables and listings. Medications will be summarized by ATC level 3 (level 3 indicates the therapeutic/pharmacologic subgroup) alphabetically and preferred name (decreasing frequency in the Gemcabene column within each ATC) by actual treatment group for the SAS. At each level of summarization, subjects who report one or more medications within a given level (eg, ATC and preferred name) will only be counted once at that level. Excluded medications will be flagged in the concomitant medications listing.

13.3 Concomitant Procedures

Concomitant procedures will be recorded on the concomitant medications CRF. A concomitant procedure is defined as a procedure with a start date on or before the date of the subject's last dose (ie, procedure start date \leq date of last dose) and a stop date on or after the date of the subject's first dose (ie, procedure stop date \geq date of first dose). Concomitant procedures will be presented in a listing containing verbatim terms for the SAS.

15 APPENDICES

Appendix 1. Schedule of Assessments and Procedures

	Pre-Screening ^a	Screening ^b		Treatment Period ^c				Follow-up ^d	ET		
		up to Day-14	Day 1 ^e	Week 2 (Day 15 ± 3 days)		Week 4 (Day 29 ± 3 days)	Week 8 (Day 57 ± 3 days)	Week 12 (Day 85, or up to 3 days earlier)		Day 113 ± 3 days	
				Visit S1	Visit T1	Visit T2	Visit T3	Visit T4			Visit T5
Informed consent	X	X ^f									
Inclusion/exclusion criteria	X	X									
Medical/surgical history and demographics	X	X ^f									
Full physical examination ^g	X	X ^f					X		X		
Symptom-directed physical examination		X ^h	X	X	X	X		X ⁱ			
Vital signs ^j , height ^k , and weight	X	X	X	X	X	X	X		X		
Body Mass Index (BMI)	X	X									
Urinalysis ^l	X	X	X		X	X	X	X ⁱ	X		
Serum/urine pregnancy test ^m	X	X	X	X	X	X	X		X		
Safety chemistry panel, coagulation, and hematology ⁿ	X	X	X	X	X	X	X	X ⁱ	X		
TSH, HbA1c, and serology ^o	X	X ^f					X		X		
Fasting lipid panel ^p ; LDL-C ultracentrifugation when necessary	X ^q	X	X	X	X	X	X		X		
Fasting apolipoproteins ^r			X		X	X	X		X		
PCSK9			X				X		X		
hsCRP, SAA, fibrinogen, and adiponectin			X				X		X		
Fasting plasma glucose, insulin			X				X		X		
Randomization			X								
Study drug administration ^s			X	X	X	X	X				
Dispense study drug and instructions			X	X	X	X					

	Pre-Screening ^a	Screening ^b		Treatment Period ^c				Follow-up ^d	ET
		up to Day-14	Day 1 ^e	Week 2 (Day 15 ± 3 days)	Week 4 (Day 29 ± 3 days)	Week 8 (Day 57 ± 3 days)	Week 12 (Day 85, or up to 3 days earlier)	Day 113 ± 3 days	
				Visit T2	Visit T3	Visit T4	Visit T5		
		Visit S1	Visit T1	Visit T2	Visit T3	Visit T4	Visit T5		
Compliance check				X	X	X	X		X
Dietary instructions ^l	X	X	X	X	X	X			
12-lead ECG ^h		X	X	X	X	X	X		X
Initiate wash-out	X								
Adverse events	X ^v	X ^v	X	X	X	X	X	X	X
Concomitant medications	X	X ^f	X	X	X	X	X	X	X
Reserve samples			X	X	X	X	X		X

Apo = apolipoprotein, BMI = body mass index, ECG = electrocardiogram, eCRF = electronic case report form, ET = Early Termination, HBV = hepatitis B virus, HbA1c = hemoglobin A1c, HCV = hepatitis C virus, HDL-C = high-density lipoprotein cholesterol, HIV = human immunodeficiency virus, HoFH = homozygous familial hypercholesterolemia, hsCRP = high sensitivity C-reactive protein, LDL-C = low density lipoprotein cholesterol, Lp(a) = lipoprotein(a), NCEP ATP-III = National Cholesterol Education Program Adult Treatment Panel III, NGAL = neutrophil gelatinase-associated lipocalin, non-HDL-C = non-high-density lipoprotein cholesterol, **CI** lipoprotein cholesterol. SAA = serum amyloid A, TC = total cholesterol, TG = triglyceride, TSH = thyroid-stimulating hormone, VLDL-C = very low density lipoprotein cholesterol.

- ^a Only subjects requiring a wash-out period will participate in the Pre-Screening Visit. Specifically, **CI** inhibitors will require an 8-week wash-out period, fibrates will require a 6-week wash-out period, and niacins or other lipid-regulating therapies such as bile acid sequestrants will require a 4-week wash-out period, prior to the Screening Visit.
- ^b All eligible subjects will participate in the Screening Visit up to 14 days prior to Day 1. For subjects taking the required stable statin therapy for > 4 weeks at the Screening Visit and do not require a wash-out period, the Screening Visit will be their first study visit.
- ^c Study assessments will be completed ± 3 days of given time point for all study visits from Day 1 through Week 8. Week 12 assessments can be performed up to 3 days prior to Week 12, but not after Week 12.
- ^d The Follow-up Visit will be conducted as a telephone call 4 weeks (± 3 days) after the last dose of study drug, unless the subject requires a site visit due to an abnormal result at Week 12 (or the ET Visit, if applicable) or an ongoing treatment-related adverse event.
- ^e Procedures will be performed pre-dose. The Investigator will inquire with the subject at Day 1 to determine if there have been any changes in the subject's health affecting eligibility or requiring an update to their medical and surgical history.
- ^f For subjects who required a wash-out period and completed the Pre-Screening Visit, the following Screening Visit procedures will not be repeated: informed consent, full physical examination, height, TSH, HbA1c, and serology (HBV, HCV, and HIV) screening. Updates, as needed, will be made to medical/surgical history, demographics, and concomitant medications.
- ^g A full physical examination includes genitourinary examination per the Investigator's discretion and does not include a rectal examination.
- ^h Only for subjects who required a wash-out period and completed the full physical examination at the Pre-Screening Visit.
- ⁱ Only for subjects who had an abnormal result at Week 12 (or the ET Visit, if applicable) or an ongoing treatment-related adverse event.
- ^j Vital signs include pulse rate, blood pressure, respiration rate, and temperature. Blood pressure should be obtained in the seated position, after the subject has rested comfortably for at least 5 minutes. Blood pressure at the Screening Visit should be obtained in both arms and the arm with the highest value should be used for ongoing

	Screening ^b		Treatment Period ^c				Follow-up ^d	ET
	Pre-Screening ^a	up to Day-14	Week 2	Week 4 (Day	Week 8	Week 12 (Day	Day 113 ± 3 days	
			(Day 15 ± 3 days)	29 ± 3 days)	(Day 57 ± 3 days)	85, or up to 3 days earlier)		
Visit S1	Visit T1	Visit T2	Visit T3	Visit T4	Visit T5			

monitoring throughout the rest of the study. If an automated assessment is performed, the same machine should be used for the subject throughout the study when possible. Care should be taken to ensure an appropriate cuff size is utilized.

- ^k Height will be measured only at the subject’s first study visit, either at the Pre-Screening Visit or the Screening Visit.
- ^l A urine microscopic examination will be performed when the dipstick result is abnormal (positive for blood, leukocyte esterase, or nitrites). Urine protein:creatinine ratio (albumin:creatinine) will be performed at the Screening Visit, Day 1, Week 4, Week 12, the Follow-up Visit (only for subjects who had an abnormal result at Week 12 [or the ET Visit, if applicable] or an ongoing treatment-related adverse event), and the ET Visit, if applicable. Urinary NGAL will be measured at Day 1, Week 4, Week 12, the Follow-up Visit (only for subjects who had an abnormal result at Week 12 [or the ET Visit, if applicable] or an ongoing treatment-related adverse event), and the ET Visit, if applicable.
- ^m For women of child-bearing potential only, a serum pregnancy test will be conducted at the Screening Visit, Week 12, and the ET Visit, if applicable. A urine pregnancy test will be conducted at the Pre-Screening Visit, Day 1, Week 2, Week 4, and Week 8.
- ⁿ Clinically significant abnormal creatinine results at Week 12 (or the ET Visit, if applicable) will also be followed-up 2 weeks (± 3 days) after the last dose of study drug in addition to the Week 4 (± 3 days) Follow-up Visit. See Appendix B in the protocol for a list of analytes and description of when repeat or reflexive testing will be required.
- ^o Thyroid-stimulating hormone, HbA1c, and serology (HBV, HCV, and HIV) will be measured at the subject’s first study visit, either at the Pre-Screening Visit, if applicable, or the Screening Visit. Only HbA1c will be measured at Week 12, and the ET Visit, if applicable.
- ^p Includes LDL-C, non-HDL-C, TC, TG, HDL-C, and VLDL-C. Fasting will be defined as no food or caloric beverage for at least 10 hours prior to sample collection. Subjects will be permitted to have water.
- ^q Includes LDL-C and TG only. Fasting will be defined as no food or caloric beverage for at least 10 hours prior to sample collection. Subjects will be permitted to have water.
- ^r Includes ApoB, ApoA-I, ApoA-II, ApoA-V, ApoC-II, ApoC-III, ApoE, and Lp(a). Fasting will be defined as no food or caloric beverage for at least 10 hours prior to sample collection. Subjects will be permitted to have water.
- ^s Study drug will be administered at the site on Day 1. Subjects will self-dose at all other times during the Treatment Period.
- ^t Subjects will be counseled on a low-fat, low-cholesterol diet (NCEP ATP-III guidelines or equivalent).
- ^u Subjects should be lying quietly in a fully supine position for at least 10 minutes prior to each 12-lead ECG.
- ^v Serious adverse events that occur prior to the first dose of study drug (Day 1) should be reported as an update to medical history as well as be reported on the appropriate adverse event eCRF.

Appendix 2. Prior and Concomitant Medications and Smoking Status Date Imputation

Imputation Rules for Partial Dates (D = day, M = month, Y = year)			
Parameter	Missing	Additional Conditions	Imputation
Start date	D only	M and Y same as M and Y of first dose of study drug	Date of first dose of study drug
		M and/or Y not same as date of first dose of study drug	First day of month
	M and D	Y same as Y of first dose of study drug Y not same as Y of first dose of study drug	Date of first dose of study drug Use Jan 01 of Y
	M, D, and Y	None - date completely missing	Day prior to date of first dose of study drug
Stop date	D only	M and Y same as M and Y of last dose of study drug	Date of last dose of study drug
		M and/or Y not same as date of last dose of study drug	Last day of month
	M and D	Y same as Y of last dose of study drug Y not same as Y of last dose of study drug	Date of last dose of study drug Use Dec 31 of Y
	M, D, and Y	None - date completely missing and NOT ongoing	Date of last dose of study drug

Note: In all cases, if an estimated start date is after a complete stop date, use the first day of the stop date month.

Similarly, if the estimated stop date is before a complete or imputed start date, use the last day of the start day month.

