Developed using Framingham Heart Study data,^{1,2} the Framingham Risk Score is an estimate of a subject's 10-year risk of developing CVD which is computed using sex-specific algorithms that contain the following risk factors: age, systolic blood pressure (SBP), smoking status, TC, HDL-C, treatment for hypertension, and diabetes status. Smoking status refers to cigarette smoking status and will be collected once for each subject during the study and recorded on the Medical History CRF. Specifically, a smoker is defined as a subject where smoking is recorded on the Medical History CRF with a start date on or before first dose (ie, smoking start date \leq day of first dose) and a stop date on or after first dose (ie, smoking stop date \geq day of first dose). Partial and missing dates will be imputed using rules in [Appendix 2](#). [Appendix 3](#) contains anatomical therapeutic chemical (ATC) categories and descriptions that will be used to identify treatment for hypertension. A subject is considered to be receiving treatment for hypertension at baseline if there is at least 1 treatment for hypertension with a start date on or before first dose (ie, medication start date \leq day of first dose) and a stop date on or after first dose (ie, medication stop date \geq day of first dose). Partial and missing dates will be imputed using rules in [Appendix 2](#). CVD comprises coronary death, myocardial infarction, coronary insufficiency, angina, ischemic stroke, hemorrhagic stroke, transient ischemic attack, peripheral artery disease, and heart failure. Please refer to [Appendix 4](#) for the sex-specific algorithms that will be used to compute each subject's Framingham Risk Score at baseline and Week 12.

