9.4 Handling of Missing Data

Missing values at baseline will not be imputed in any situation. For efficacy analyses, values missing post-randomization will be imputed using LOCF (unless otherwise specified); only post-randomization values on treatment will be used for imputation. For example, if a subject has Week 12 efficacy parameters measured more than 2 days after their last dose, their Week 12 efficacy values will be imputed using the last non-missing value while on treatment (eg, Week 8). The imputed values will be used in summaries and analysis. For safety analyses, observed case data will be used.

Imputation will not be conducted for AEs missing severity or relationship to study medication. AEs missing severity will be excluded from summaries of AEs by severity. Adverse events missing relationship will be excluded from summaries of related AEs.

Rules for partial and missing dates for prior and concomitant medications and smoking status are given in [Appendix 2](#).

Drug interruptions with partial start and/or stop dates will be assumed to be 1 day in length, and will be assumed to have occurred in the visit interval prior to when the interruption was collected (eg, if a drug interruption with partial dates was collected at the Week 8 visit, we will assume that the interruption occurred between the previous visit [eg, Week 4] and the Week 8 visit).

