Appendix 3. ATC Categories and Descriptions of Hypertensive Treatments

The WHO Drug Dictionary version 01 Mar 2016 was used to identify the following ATC categories and descriptions which will be used to identify hypertensive treatment.

ATC2/ATC2 Description ¹	ATC3/ATC3 Description	ATC4/ATC4 Description
C02/ANTIHYPERTENSIVES	C02A/ ANTIADRENERGIC AGENTS, CENTRALLY ACTING	C02AA/ Rauwolfia alkaloids
C02/ANTIHYPERTENSIVES	C02A/ ANTIADRENERGIC AGENTS, CENTRALLY ACTING	C02AB/Methyldopa
C02/ANTIHYPERTENSIVES	C02A/ ANTIADRENERGIC AGENTS, CENTRALLY ACTING	C02AC/Imidazoline receptor agonists
C02/ANTIHYPERTENSIVES	C02B/ANTIADRENERGIC AGENTS, GANGLION-BLOCKING	C02BA/Sulfonium derivatives
C02/ANTIHYPERTENSIVES	C02B/ANTIADRENERGIC AGENTS, GANGLION-BLOCKING	C02BB/Secondary and tertiary amines
C02/ANTIHYPERTENSIVES	C02B/ANTIADRENERGIC AGENTS, GANGLION-BLOCKING	C02BC/Bisquaternary ammonium compounds
C02/ANTIHYPERTENSIVES	C02C/ANTIADRENERGIC AGENTS, PERIPHERALLY ACTING	C02CA/Alpha-adrenoreceptor antagonists
C02/ANTIHYPERTENSIVES	C02C/ANTIADRENERGIC AGENTS, PERIPHERALLY ACTING	C02CC/Guanidine derivatives
C02/ANTIHYPERTENSIVES	C02D/ARTERIOLAR SMOOTH MUSCLE, AGENTS ACTING ON	C02DA/Thiazide derivatives
C02/ANTIHYPERTENSIVES	C02D/ARTERIOLAR SMOOTH MUSCLE, AGENTS ACTING ON	C02DB/Hydrazinophthalazine derivatives
C02/ANTIHYPERTENSIVES	C02D/ARTERIOLAR SMOOTH MUSCLE, AGENTS ACTING ON	C02DC/Pyrimidine derivatives
C02/ANTIHYPERTENSIVES	C02D/ARTERIOLAR SMOOTH MUSCLE, AGENTS ACTING ON	C02DD/Nitroferricyanide derivatives
C02/ANTIHYPERTENSIVES	C02D/ARTERIOLAR SMOOTH MUSCLE, AGENTS ACTING ON	C02DG/Guanidine derivatives
C02/ANTIHYPERTENSIVES	C02K/OTHER ANTIHYPERTENSIVES	C02KA/Alkaloids, excl. rauwolfia
C02/ANTIHYPERTENSIVES	C02K/OTHER ANTIHYPERTENSIVES	C02KB/Tyrosine hydroxylase inhibitors
C02/ANTIHYPERTENSIVES	C02K/OTHER ANTIHYPERTENSIVES	C02KC/MAO inhibitors
C02/ANTIHYPERTENSIVES	C02K/OTHER ANTIHYPERTENSIVES	C02KD/Serotonin antagonists
C02/ANTIHYPERTENSIVES	C02K/OTHER ANTIHYPERTENSIVES	C02KW/Herbal antihypertensives, other
C02/ANTIHYPERTENSIVES	C02K/OTHER ANTIHYPERTENSIVES	C02KX/Antihypertensives for pulmonary arterial hypertension
C02/ANTIHYPERTENSIVES	C02L/ANTIHYPERTENSIVES AND DIURETICS IN COMBINATION	C02LA/Rauwolfia alkaloids and diuretics in combination
C02/ANTIHYPERTENSIVES	C02L/ANTIHYPERTENSIVES AND DIURETICS IN COMBINATION	C02LB/Methyldopa and diuretics in combination

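### The SAP's date-imputation rule scores a former smoker with no recorded quit date as a current smoker in the Framingham Risk Score

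*SAP*

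**What the plan says.** Three parts of the SAP combine.

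- **Definition.** Section 6.2 states that "a smoker is defined as a subject where smoking is recorded on the Medical History CRF with a start date on or before first dose", and adds a second condition: the stop date must fall on or after first dose. The same section says: "Smoking status refers to cigarette smoking status and will be collected once for each subject during the study". The source is the Medical History CRF.
- **Missing dates.** Section 9.4 says: "Rules for partial and missing dates for prior and concomitant medications and smoking status are given in" Appendix 2. Medications and smoking therefore share one set of rules.
- **Stop-date rule.** When the stop date is "date completely missing and NOT ongoing", Appendix 2 inserts the date of last dose. If only the year is known, it inserts the last dose date when that year is the year of last dose, and 31 December otherwise. If only the day is missing, it inserts the last dose date when the month and year match those of last dose, and the last day of the month otherwise.

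Sections 9.3 and 11.2 use smoking status at Day 1 for both the baseline and the Week 12 score. Section 11.2 summarizes the score and its change descriptively by randomized group.

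**The concern.** For a concomitant medication with no stop date, assuming that use lasted until last dose is an ordinary cautious choice. For smoking, the same rule reverses a known fact. The entry already says that the subject has stopped; only the date is unknown.

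Timing makes the reversal likely to be wrong. Protocol Section 8.10 has medical history recorded at Pre-Screening or Screening, with an inquiry about changes at Day 1. An entry of not ongoing on a form filled in then normally means that the subject quit before dosing. The rule moves the quit date to the end of treatment.

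What is at stake is one secondary endpoint. Change in Framingham Risk Score serves the cardiovascular-risk part of the secondary objectives. With NCEP ATP-III risk dropped in SAP Section 8, it is the only risk score left among the listed secondary measures.

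**Working it through.** The documents give no figure to reproduce. The check has two steps: apply the rules to test records, then see how far one wrong flag moves the score.

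**Step 1: the rules.** Inputs are the smoker definition (start ≤ first dose ≤ stop) and Appendix 2. Assumed dates: first dose 15 February 2017, last dose 10 May 2017 (85 days). The start year is 1980 except in the second row.

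| Smoking record | Imputed stop | Status at Day 1 |
|---|---|---|
| Not ongoing, stop wholly missing | 10 May 2017 | Smoker |
| Not ongoing, start and stop both missing | 10 May 2017 (start imputed as 14 February 2017) | Smoker |
| Quit 2017, month and day missing | 10 May 2017 | Smoker, even if the subject quit in January |
| Quit February 2017, day missing | 28 February 2017 | Smoker, even if the subject quit before the 15th |
| Quit January 2017, day missing | 31 January 2017 | Non-smoker |
| Quit 2016, month and day missing | 31 December 2016 | Non-smoker |
| Quit 2005, month and day missing | 31 December 2005 | Non-smoker |

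With one day of exposure, last dose equals first dose, and the first two rows still give a smoker. For a wholly missing stop date the result therefore does not depend on the dates chosen. If dosing runs across a new year and the known quit year is that of first dose, the imputed 31 December again falls on or after first dose and gives a smoker.

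**Step 2: effect on one subject's score.** Appendix 4 gives risk = 1 − S0^exp(LP), where LP is the sum of coefficients times centered risk factors. Wrongly setting a yes/no factor multiplies the exponent by its hazard ratio HR. With true risk p:

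- scored risk = 1 − (1 − p)^HR
- for a fall in hazard to 0.9 of its baseline value, true change = [1 − (1 − p)^0.9] − p
- scored change = [1 − (1 − p)^(0.9·HR)] − [1 − (1 − p)^HR]

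The available text of Appendix 4 shows no coefficients, so HR is an assumption. So are the 10% fall in hazard and the starting risk. At p = 10%:

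- HR 1.5: 1 − 0.9^1.5 = 14.6%
- HR 2.0: 1 − 0.9^2 = 19.0%
- true change: (1 − 0.9^0.9) − 0.10 = −0.95 points
- scored change at HR 1.5: (1 − 0.9^1.35) − (1 − 0.9^1.5) = −1.36 points, ratio 1.43
- scored change at HR 2.0: (1 − 0.9^1.8) − (1 − 0.9^2) = −1.72 points, ratio 1.81

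Over a wider assumed range of HR, 1.25 to 2.5, the scored risk runs from 12.3% to 23.2% and the scored change from −1.16 to −2.05 points.

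**Step 3: dilution in the group mean.** If 5% of subjects were affected (an assumption) and their true change were typical, the mean change would be multiplied by 1 + 0.05 × 0.43 = 1.02 at HR 1.5 and by 1 + 0.05 × 0.81 = 1.04 at HR 2.0.

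**The case against.** The best defense is that little depends on this.

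- **Few records should reach the rule.** Protocol Section 10.1.5 sends missing data back to the site as queries, and Section 10.1.1 treats an eCRF as complete only when missing items are accounted for. A quit year well before the trial, with a known earlier start, is handled correctly. The CRF is not among the documents, so it is unknown whether it allows not ongoing without a date. This stands as a limit on the number affected. It does not alter what the rule does with the records that remain.
- **The consequence is contained.** The smoking flag is the same at both time points, the rule is the same in both blinded arms, and the score is only described. This stands, and it is why the point is minor.

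A reader might infer more than the documents support:

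- **That the treatment comparison is biased.** A Day 1 flag set by one rule in both randomized arms gives no reason to expect that.
- **That men's risk rises from 11.1% (1 − 0.88936).** In Appendix 4 that figure is the risk with every factor, smoking included, at its mean. It is not a non-smoker's risk, which is why the working starts from a chosen true risk.
- **That the same rule wrongly keeps a stopped antihypertensive in the Week 12 score.** Protocol Section 5.6.4 records medications through the Follow-up Visit, so the undated stop may truly follow last dose. Counting the drug as stopped at Week 12 while it still counts at baseline would create a false fall in risk.
- **That the ATC list in Appendix 3 is wrong because it ignores indication.** It does ignore it, and it includes "C02KX/Antihypertensives for pulmonary arterial hypertension". But a prespecified class list is a reproducible definition. Requiring hypertension in Medical History would misclassify too: it would miss unrecorded hypertension and still count a beta blocker taken for angina by a hypertensive subject. Nothing indicates that any subject takes the pulmonary hypertension class.

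**Conclusion.** The smoking rule is wrong as written. A record marked not ongoing with no stop date, and a start date on or before first dose, always becomes current smoking. A partial stop date can have the same effect when the known year is that of last dose, or when the known month or year contains first dose. This follows from Section 6.2 and Appendix 2 alone.

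The affected subject's risk level is too high at both visits and the change is scaled up, by roughly 1.4 to 1.8 times under the assumed hazard ratios at a true risk of 10%. The flag cannot produce a change where none exists. The error should not favor either arm, and it reaches only a descriptive secondary endpoint. The hazard ratios, the starting risk, the 10% fall in hazard and the 5% share are all illustrative, and the true number affected is unknown. Severity: minor.

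**What to change.** In Appendix 2, take smoking out of the medication stop-date rule and add one sentence: if smoking is recorded as not ongoing and the stop date is missing or partial, the subject is a non-smoker at Day 1 unless the known part of the date places the stop after first dose. Point to that sentence from Section 6.2.

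The cost is a line of text and a small programming change, using data already collected. The downside is also small: a subject who quit between first and last dose, without a date that shows it, would be classed as a non-smoker. Because smoking is collected once on the Medical History CRF, few such records are to be expected. The hypertension-treatment rules and the Appendix 3 list need no change on this account.
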